7.6.6.4 Retreatment intervals

For both the DBPC Cycle and by the Dysport Cycles, summary statistics will be displayed for time between treatments received, time to request and time to eligibility for retreatment. For the DBPC Cycle the number and percentage of patients receiving retreatment: \geq Week 12 to $<$ Week 16, \geq Week 16 to $<$ Week 20 weeks and then every 4 weeks will be presented.

The following formal statistics will be performed only for the time between treatments received endpoint. For both the DBPC Cycle and by the Dysport Cycles, median number of days together with the 25th and 75th percentiles and their 95% CI will be determined based on the Kaplan-Meier method. Patients with no retreatment will be censored at the last visit. The survival curves will be presented by treatment group as well.

For the DBPC and Dysport treatment cycles, the log-rank tests will be performed to compare survival curves between treatment groups, by providing p-values.

The SAS codes of survival analysis for reference are below.

CCI
[Redacted SAS code]

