7.6.6 Other Analysis of Secondary Efficacy Endpoints

The analysis of efficacy of the above-mentioned endpoints (primary endpoint and secondary endpoints included in the hierarchical analysis) will be conducted at timepoints other than Week 6 in the DBPC Cycle and is described below (except urodynamic endpoints as only performed at Week 6). The analysis of other secondary endpoints (see Section 3.2) is also described below.

Descriptive summaries will be performed for the DBPC Cycle and by Dysport Cycles (i.e. Dysport Cycle 1, Dysport cycle 2 ...), see the schematic diagram in Section 7.1.

Statistical comparison analyses are only applicable for the DBPC treatment cycle. Analyses between treatment groups, Dysport 600 U vs. Placebo, and Dysport 800 U vs. Placebo will be performed accordingly using GLMM and MMRM as mentioned below for each endpoint. As all subjects should have visits up to and including week 12, but thereafter visits are dependent on whether the subject receives retreatment, statistical testing between treatment groups will be

performed only up to Week 12, inclusive. All secondary endpoints not included in the hierarchical analysis are considered as exploratory endpoints and will therefore be analysed for exploratory purposes only to compare each Dysport dose to placebo, alpha at 0.05 level.

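### SAP 7.6.6.4 drops survival analysis for two of the three duration-of-effect endpoints without declaring it, and orders Dysport-cycle log-rank tests that SAP 7.6.6 rules out

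*SAP*

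**What the plan says.** **Protocol.** Section 9.4.5 names time to retreatment request, time to eligibility and time between treatments as secondary variables. It assigns time-to-event data to survival methods, shown in summary tables and Kaplan-Meier plots, and mentions log-rank statistics among the methods. Table 19 asks for the mean and median number of days for each. It counts a request only if the subject is later found eligible.

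**SAP 7.6.6.4.** For both the DBPC (double-blind placebo-controlled) cycle and the Dysport cycles, "summary statistics will be displayed for time between treatments received, time to request and time to eligibility for retreatment". Then: "The following formal statistics will be performed only for the time between treatments received endpoint". The Kaplan-Meier quartiles, the survival curves and the only censoring rule, "Patients with no retreatment will be censored at the last visit", come after that restriction. On testing: "For the DBPC and Dysport treatment cycles, the log-rank tests will be performed to compare survival curves between treatment groups".

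**SAP 7.6.6 (parent section).** "Statistical comparison analyses are only applicable for the DBPC treatment cycle". It continues: "Analyses between treatment groups, Dysport 600 U vs. Placebo, and Dysport 800 U vs. Placebo will be performed accordingly using GLMM and MMRM", with the method deferred to the endpoint subsections, and between-group testing "performed only up to Week 12, inclusive".

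**SAP Section 8** on changes in planned analyses is marked as not applicable. SAP 3.2 places the detailed endpoint definitions in Appendix II, which is not public.

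**The concern.** Duration of effect is part of two secondary objectives. Follow-up ends between Weeks 104 and 116, so some subjects may never make a qualifying request. A plain mean or median has no place for them. The subjects left out are mainly those in whom the effect lasted longest, so the summary understates duration, and more so in the longer-lasting arm. The protocol's survival methods avoid this.

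The second problem is internal to the SAP. One sentence orders between-group p-values in the Dysport cycles, and its parent section says such comparisons do not apply there. Whoever programs the analysis must choose which sentence to follow.

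**Working it through.** The plan gives no event counts, medians or power for these endpoints, so there is no figure of its own to reproduce.

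**1. Protocol 9.4.5 against SAP 7.6.6.4**

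| Endpoint | Protocol 9.4.5 | SAP 7.6.6.4 |
|---|---|---|
| Time between treatments | survival methods | Kaplan-Meier, censoring rule, log-rank |
| Time to request | survival methods | summary statistics only |
| Time to eligibility | survival methods | summary statistics only |

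SAP 7.1 defines summary statistics as n, mean, SD, median, minimum and maximum. No visible text says how a subject without the event enters them. The SAP's summary of changes explains the empty Section 8 by saying that the protocol amendment carries all the changes, but the current protocol still calls for survival methods.

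**2. Size of an event-only median**

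Assumed, not in the documents: T = 12 weeks + exponential with true median m, everyone followed to Week 104, and summaries using only subjects with the event.

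- Share without the event: c = 2^(−92/(m−12)), since 104 − 12 = 92.
- Event-only median: 12 + (m−12) × log2[1/(1 − (1−c)/2)].
- Example, m = 44: c = 2^(−92/32) = 0.136; 1 − 0.864/2 = 0.568; log2(1/0.568) = 0.816; 12 + 32 × 0.816 = 38.1; difference −5.9.

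| True median (weeks) | Without event | Event-only median | Difference |
|---|---|---|---|
| 20 | 0.0% | 20.0 | 0.0 |
| 26 | 1.1% | 25.8 | −0.2 |
| 32 | 4.1% | 30.8 | −1.2 |
| 39 | 9.4% | 35.5 | −3.5 |
| 44 | 13.6% | 38.1 | −5.9 |
| 52 | 20.3% | 41.3 | −10.7 |

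Two arms with true medians of 32 and 44 weeks differ by 12 weeks. Event-only medians would show 38.1 − 30.8 = 7.3.

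Two variations, also on assumed inputs:
- SAP 7.8 plans an analysis at a data cut whose trigger is redacted. With follow-up uniform over 52 to 104 weeks, simulation gives −0.1, −1.0, −3.2 and −10.4 weeks at true medians 20, 26, 32 and 44.
- With 10 to 30% dropout over two years, a true median of 300 days is summarised as 248 to 258 days, which is 6.0 to 7.4 weeks too short.

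A Kaplan-Meier analysis of qualifying requests, with pending ones censored, stays within 0.2 weeks of the true median both for follow-up to Week 104 and for the 52-to-104-week cut.

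**3. How closely the retained endpoint tracks the others**

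The protocol gives ideal windows of 14 days from request to the assessment visit and 14 days from confirmed eligibility to retreatment. Retreatment therefore trails the request by at most 14 + 14 = 28 days, or 4 weeks, and eligibility by at most 2 weeks, if the windows hold. With each delay taken as uniform over 0 to 14 days, the retained Kaplan-Meier median lies 1.8 to 2.1 weeks above the true request median in every case run.

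**4. SAP 7.6.6 against SAP 7.6.6.4**

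In the Dysport cycles no placebo group remains, so the log-rank test can only compare 600 U with 800 U. SAP 7.6.6 restricts comparisons to the DBPC cycle and states no exception.

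**The case against.** **Against the first mismatch.** Table 19 asks for means and medians, which plain summaries deliver. The protocol leaves analysis detail to the SAP, and Appendix II may contain a rule for subjects without the event. The n is reported, and "For the DBPC Cycle the number and percentage of patients receiving retreatment" is tabulated in 4-week bands, so a reader can see how many subjects had the event. All of this stands and limits the consequence. It does not remove the mismatch: the protocol sets the method, a Kaplan-Meier median is still a median, and nothing visible declares the narrowing.

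**Against the second.** A reader might infer that even the DBPC log-rank test conflicts with SAP 7.6.6, because it is neither GLMM nor MMRM and its events fall after Week 12. Retreatment needs more than 84 days; Week 12 is Day 85, which is 84 days after Day 1, so the earliest whole day is Day 86. The documents do not support that inference. SAP 7.6.6 defers methods to the subsections, and SAP 7.6.6.2 under the same heading uses logistic regression. The Week 12 limit is justified by visits that depend on retreatment, which concerns visit-based measures. Protocol 9.4.5 itself names log-rank statistics. Nor can one fault the plan for leaving contrasts unnamed, since the survival code that could show them is redacted.

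A reader might also infer that Dysport Cycle 2 tests are shown to be invalid, because entry and remaining follow-up depend on earlier cycle length. Simulated rejection at a nominal 5%, with equal Cycle 2 durations, is 4.8 to 5.8% if Cycle 1 doses do not differ or durations are uncorrelated within subject. It is 5.5 to 6.4% for Cycle 1 medians of 36 v 44 weeks with correlation 0.3, and 6.9 to 10.0% with 0.6. Higher rates need a larger Cycle 1 dose difference that vanishes in Cycle 2. The documents give none of these inputs, so this supports a caution and is not evidence of an error in the plan.

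**Conclusion.** Two textual mismatches hold. SAP 7.6.6.4 limits Kaplan-Meier and its censoring rule to one of three duration endpoints, against protocol 9.4.5 and without a declared change. It also orders Dysport-cycle log-rank p-values that SAP 7.6.6 excludes. The DBPC log-rank agrees with the protocol and needs at most a clarifying phrase in 7.6.6.

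The understatement of duration is conditional on Appendix II holding no rule for subjects without the event and on censoring being material. Under the assumed model with follow-up to Week 104 it is 0 to 1.2 weeks at true medians up to 32 weeks, 5.9 at 44 and 10.7 at 52. Severity is minor. SAP 7.6.6 classes these endpoints as exploratory, so no confirmatory claim is touched, and the retained Kaplan-Meier endpoint gives a close substitute if the ideal visit windows hold.

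**What to change.** (a) In SAP 7.6.6.4, analyse time to request (event as in protocol Table 19) and time to eligibility by Kaplan-Meier, censoring subjects without the event at the last visit. Report medians with 95% confidence intervals, and label any event-only mean or median as such, with its n. If Appendix II already holds such a rule, cross-refer to it and correct the word *only*.

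(b) Reconcile SAP 7.6.6 with 7.6.6.4. Either drop the Dysport-cycle log-rank p-values, or state an exception in 7.6.6 that labels them exploratory 600 U v 800 U comparisons. The exception should caution that from Dysport Cycle 2 onward entry and remaining follow-up depend on earlier cycle length. A phrase confirming that the Week 12 and GLMM/MMRM wording applies to visit-based endpoints would remove any doubt about the DBPC test.

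Cost: SAP wording and a few more tables. The request, eligibility, retreatment and last-visit dates are already needed for the planned summaries, so no new data are required.

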5 STUDY PROCEDURES

5.1 Study Schedule

The schedule of procedures and assessments during the study is summarised in [Table 4](#) for Screening and Treatment 1 follow-up and in [Table 5](#) for retreatment assessment and follow-up.

Table 4 Study Procedures and Assessments for First Treatment and Follow-Up Until Retreatment or End Of Study

	Screening		Treatment	Post-Treatment 1 Follow-up						End of Study/ Withdrawal
	Screening Visit 1	Screening Visit 2 [h][p]	Treatment Visit (Day 1) [h]	Week 1 Visit (Day 8)	Week 2 Visit (Day 15)	Week 4 Visit (Day 29)	Week 6 Visit (Day 43)	Week 12 Visit (Day 85)	Routine Visit every 12 weeks (84 days) until retreatment occurs	End of Study Visit (Week 104 to Week 116) [o]
	Clinic	Clinic	Clinic	Telepho ne [m]	Clinic	Telepho ne [m]	Clinic	Clinic	Telephone [m]	Clinic
Visit window (days)	-30 to -1 [p]		Within 14 days of Screening Visit 2 [h]	±3 days	±3 days	±3 days	±3 days	±7 days	±14 days	±14 days
Informed consent	X									
Demographic data	X									
Medical/surgical/NDO history	X									
Prior medications and therapies	X									
Inclusion/exclusion criteria	X	X	X							
Concomitant medications and therapies	X	X	X	X	X	X	X	X	X	X
Prior and concomitant treatments for NDO [a]	X	X	X	X	X	X	X	X	X	X
Adverse events	X	X	X	X	X	X	X	X	X	X
Physical examination (symptom-based)	X						X			X
Vital signs	X [f]		X [l]		X		X	X		X
Urinary tract ultrasound	X [g]									
Urine pregnancy test [b]	X		X							
Laboratory urinalysis/microscopy [c]	X						X	X		X
Urine culture [c]	X						X			
Dispense antibiotics		X [i]					X [n]			
Haematology and serum chemistry	X						X			X
Anti BTX-A antibodies	X						X			X
Dispense bladder diary & training [d]	X									
Bladder diary review		X [j]			X [j]		X [j]	X [j]	X [j]	X [j]
I-QoL and EQ-5D-5L			X				X	X		X
mPGI-I [e]					X		X	X	X	X
Urodynamics (filling cystometry)		X [k]					X			
Randomisation			X							
IMP administration			X							

BTX-A=botulinum toxin type A; EOS=End of Study; EQ-5D-5L=EuroQoL 5-dimension 5-level; IMP=investigational medicinal product; I-QoL=incontinence quality of life; mPGI-I=modified patient global impression - improvement; NDO=neurogenic detrusor overactivity.

-
- a Concomitant treatments for NDO (e.g. anticholinergics, beta-3 agonists, clean intermittent catheterisation rate) should remain stable during the first 12 weeks after Treatment 1 (preferably for the entire duration of the study).

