15.2 Clinical Study Report

In order to support regulatory submission an ICH E3-compliant clinical study report (CSR) may be prepared prior to completion of the study. See [Section 9.6](#) for details regarding this primary analysis.

A final CSR will be prepared according to the ICH guideline on structure and contents of CSRs. A final CSR will be prepared where any subject has signed informed consent, regardless of whether the study is completed or prematurely terminated. Where appropriate an abbreviated report may be prepared. The CSR will be in compliance with any applicable regulatory requirements, national laws in force and will be in English.

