The Treatment Visit (Day 1) should occur up to 14 days after the screening period, but can be extended until the UTI is resolved (where a UTI has occurred and impacts the ability to perform IMP administration). At the Treatment 1 visit on Day 1, subjects who meet all the eligibility criteria will be randomised (in a 2:2:1:1 ratio) to one of four treatment sequences:

Statistical Analysis Plan

Version: Final v2.0

September-2018

Ipsen Protocol No. D-FR-52120-222

000000146259

Date of Issue: 21-

Covance Study ID:

Sequence	Subjects	1 st Treatment in DBPC Cycle	Subsequent retreatment(s) in Dysport Cycles (Dysport Cycle 1, Dysport Cycle 2, etc)
1	110 subjects	Dysport 600 U	Dysport 600 U
2	110 subjects	Dysport 800 U	Dysport 800 U
3	55 subjects	Placebo	Dysport 600 U
4	55 subjects	Placebo	Dysport 800 U

During the analysis of DBPC cycle, the two placebo containing sequences will be pooled into a single arm.

Randomisation will be stratified by;

- Aetiology of NDO (SCI or MS)
- Previous intradetrusor botulinum toxin type A (BTX-A) usage (BTX-A naïve vs. BTX-A non-naïve).

Follow-up (after IMP administration in DBPC cycle):

- Week 1 (Day 8) (telephone)
- Week 2 (Day 15) (clinic visit)
- Week 4 (Day 29) (telephone)
- Week 6 (Day 43) (clinic visit; primary timepoint)
- Week 12 (Day 85) (clinic visit; the retreatment could be requested by subject from this visit)
- Every 12 weeks (telephone visits; until retreatment received or end of study (EOS) at Weeks 104 to 116).

Details of the procedures performed at each visit following the first treatment are shown in the schedule of assessments, [Appendix V](#).

Retreatment assessment

A subject may request retreatment with IMP at any time ≥ 12 weeks after their most recent study treatment.

The retreatment criteria are as follows:

- 1) Retreatment requested by subject;
- 2) More than 12 weeks (84 days) since the previous IMP administration;
- 3) CCI [REDACTED]
- 4) [REDACTED]
- 5) In the investigator's opinion it is safe and appropriate to provide retreatment.

Statistical Analysis Plan

Version: Final v2.0

September-2018

Ipsen Protocol No. D-FR-52120-222

000000146259

Date of Issue: 21-

Covance Study ID:

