7.8 Primary Analysis of the Study

CCI [REDACTED]
[REDACTED]
[REDACTED]
[REDACTED]

[REDACTED]. The analysis will consist of all tables, figures and listings for the study described in this statistical analysis plan using all available data up to the cut-off date and a clinical study report will be written. A final analysis will occur when all subjects have completed the study (or at other timepoints if required to support regulatory agency submissions).

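### Censoring unretreated subjects at their last visit biases the Kaplan-Meier time between treatments short in any analysis run before study completion

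*SAP*

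**What the plan says.** SAP 7.6.6.4 gives summary statistics for three duration measures and keeps inference for one of them: "The following formal statistics will be performed only for the time between treatments received endpoint". That inference is Kaplan-Meier medians and quartiles with confidence intervals, plus log-rank tests between treatment groups, for the DBPC Cycle and each Dysport Cycle. The only visible censoring rule is "Patients with no retreatment will be censored at the last visit". It does not separate subjects still in follow-up from those who withdrew or completed.

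SAP 7.8 applies all tables and figures to a primary analysis "using all available data up to the cut-off date and a clinical study report will be written". It then says "A final analysis will occur when all subjects have completed the study". Protocol 15.2 confirms the order: "In order to support regulatory submission an ICH E3-compliant clinical study report (CSR) may be prepared prior to completion of the study".

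After Week 12 the schedule is "Every 12 weeks (telephone visits; until retreatment received or end of study (EOS) at Weeks 104 to 116" (SAP 2.2). Retreatment is not tied to those visits: "A subject may request retreatment with IMP at any time ≥ 12 weeks after their most recent study treatment" (SAP 2.2).

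**The concern.** Kaplan-Meier estimation needs the censoring time to be unrelated to the event, given survival so far. At a pre-completion cut-off the SAP rule breaks this for subjects still in follow-up.

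Take two subjects whose last routine visit was Week 36 and whose cut-off falls 46 weeks after treatment. One is retreated at Week 42 and enters as an event at 42. The other is not retreated and is removed at 36, although 46 - 36 = 10 further event-free weeks were observed. The second subject is missing from the risk set at Week 42 only because no event occurred. Errors of this kind run one way, towards shorter duration.

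Duration of effect is part of two secondary objectives (Protocol 2.2), and the affected output is the report that may support regulatory submission. At stake is a modest understatement of how long a treatment lasts.

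**Working it through.** **No figure to reproduce.** The documents give no expected median, event count or power for this endpoint. What follows measures the size of the bias under stated assumptions.

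**The mechanism in small numbers (invented).** Suppose 10 subjects are event-free at their Week 36 visit and 2 are retreated before a cut-off at Week 46. With cut-off censoring, the proportion still unretreated across that interval is 8/10 = 0.80. Under the SAP rule the 8 leave the risk set at Week 36. The 2 events then occur in a risk set of 2, and the estimate for this group falls to 0. In the trial, subjects with longer follow-up dilute the effect, so its size has to be simulated.

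**Inputs from the documents**
- Visits at Weeks 1, 2, 4, 6 and 12, then every 12 weeks from each treatment (SAP 2.2).
- No event before 12 weeks and no retreatment after Week 104 (SAP 2.2).
- End-of-study visit at Week 104, or 12 weeks after a treatment given after Week 92 (SAP 2.2).
- Study period first quarter 2016 to last quarter 2020 (Protocol synopsis). Mid-quarter to mid-quarter is 4.75 years, and 4.75 × 52 = 247 weeks. Less 116 weeks of follow-up, this leaves about 131, so accrual is set near 130 weeks.

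**Assumed**
- Interval = 12 weeks + a Weibull time (shape 1 unless stated).
- Uniform accrual, and 10% withdrawal over 104 weeks with a withdrawal visit.
- Cut-off a set number of weeks after last entry.
- Each subject's successive intervals independent, unless stated.

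Both versions count retreatments to the cut-off as events. They differ only in the censoring date of ongoing subjects. Cycle 1 means the first study treatment.

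**Result: accrual 130 weeks, cut-off 12 weeks after last entry, true median 40 weeks**

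| Cycle | Censored at cut-off | Censored at last visit | Shift (weeks) |
|---|---|---|---|
| 1 | 39.8 | 38.5 | -1.3 |
| 2 | 40.1 | 38.2 | -1.9 |
| 3 | 39.6 | 37.2 | -2.4 |

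A second run of this setting gave shifts of 1.4, 1.9 and 2.3 weeks, so simulation error is about 0.1 week.

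**Sensitivity**
- *True median:* in Cycle 1 the shift is -0.4 week at a true median of 20, -0.9 at 30 and -1.9 at 50.
- *Hazard shape:* with shape 2 and a true median of 40, the shifts in Cycles 1/2/3 are -0.7, -1.1 and -1.3.
- *Wider grid:* over 144 scenarios (accrual 90 to 150 weeks, cut-off 6 to 52 weeks, true median 20 to 50, shape 1 to 2), the typical shift in Cycles 1/2/3 is -0.4, -0.9 and -1.2 weeks. The extremes, -3.5, -7.4 and -12.5, need short accrual, an early cut-off and long intervals.
- *Late cut-off:* at 52 weeks after last entry every subject has at least 52 weeks from first treatment, so an ongoing subject's last routine visit in Cycle 1 is no earlier than Week 4 × 12 = 48. That lies beyond a median of 40, and the shift in Cycle 1 is 0.0.
- *Final analysis:* the last visit is then the end-of-study or withdrawal visit, and the shift is 0.0 in every cycle.

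**Dependence on independent intervals.** Same setting (accrual 130, cut-off 12 weeks, median 40), with a gamma-distributed subject effect added:

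| Variance of subject effect | Bias in Cycles 1 / 2 / 3 (weeks short) |
|---|---|
| 0 | 1.4 / 1.9 / 2.3 |
| 0.25 | 1.6 / 1.7 / 1.9 |
| 0.5 | 1.6 / 1.8 / 1.7 |
| 1 | 1.9 / 1.4 / 0.9 |

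The bias stays in every row. Its pattern over cycles does not.

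**The case against.** The strongest case on the other side is that this is small and may not arise.

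- *Size.* With 110 subjects in Cycle 1 and a true median of 40 weeks, the sampling standard deviation of the Kaplan-Meier median is about 4.2 weeks, against a shift of about 1.4. The endpoint is outside the testing hierarchy and exploratory (SAP 7.6.2 and 7.6.6). This stands and sets the priority. It does not remove the bias, which runs one way and does not shrink with sample size.
- *Hidden text.* The cut-off trigger (SAP 7.8, Protocol 9.6) and the survival code are redacted, and the endpoint definitions in SAP Appendix II are not shown. Any of these could define the last visit differently or place the cut-off late enough to spare the first cycle. This also stands: the point rests on the visible text.
- *Completeness of records.* Cut-off censoring is unbiased only if every retreatment to that date is in the data. The IRT allocates a treatment number at each dispensing (Protocol 3.3.1), but no passage says those records feed this endpoint. If site entry lags, the bias would run towards longer duration. The fix therefore has to name a date to which retreatment status is complete.

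Two stronger readings are tempting. A reader might infer that the bias is always larger in later cycles. That follows when a subject's successive intervals are independent, but in the 12-week cut-off setting it flattens or reverses once subjects differ, and the documents say nothing on this. A reader might also infer that the rule creates a false impression of effect waning with repeated treatment. With a subject-effect variance of 0.25, the median falls from Cycle 1 to Cycle 3 by 38.2 - 31.4 = 6.8 weeks under the SAP rule and by 39.8 - 33.3 = 6.5 weeks with cut-off censoring. At the final analysis, where the censoring bias is zero, it still falls by 40.0 - 33.9 = 6.1 weeks. Most of that decline is selection: subjects with short intervals are the ones who reach later cycles by Week 104. The SAP plans no test between cycles.

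**Conclusion.** The concern holds for any analysis at a cut-off before study completion. As written, the rule makes censoring depend on the outcome for ongoing subjects and biases the Kaplan-Meier median short.

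Under 130-week accrual, a true median of 40 weeks, constant hazard after Week 12 and a cut-off 12 to 26 weeks after last entry, the shift is about 1 to 2 weeks (2.4 in the third cycle in one run with independent intervals). Accrual, interval distribution and cut-off are all assumptions. For a cut-off 52 weeks after last entry the first treatment cycle shows about zero bias. That result carries over to the DBPC Cycle but not fully to Dysport Cycle 1, which also contains later-starting cycles from the placebo sequences (SAP 7.1). The final analysis is unaffected.

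No confirmatory conclusion changes. The effect on the log-rank test was not computed; all arms follow the same rule. The documents do not support a general claim that the bias grows over cycles, or that it explains any apparent waning. The change is worth making because it removes an avoidable bias cheaply.

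**What to change.** In SAP 7.6.6.4, replace the censoring sentence with:

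> Subjects without a retreatment who are still in follow-up at the data cut-off are censored at the cut-off date (the date to which retreatment status is complete, with events counted to the same date), and no later than the last day on which retreatment is permitted. Subjects who withdrew or completed are censored at their withdrawal or EOS visit.

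Apply it to the DBPC Cycle and every Dysport Cycle, and align the survival code and Appendix II if they say otherwise.

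The cost is one sentence and one derived date, with no new data collection. The small downside is that retreatment records must be reconciled to the cut-off date, for example against IRT dispensing. The change does not address selection into later cycles, so comparisons of medians across cycles still need that caution in the report.
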